An *a priori* computer-generated stratified block randomization list will be used to assign patients to each of the 4 parallel fixed dosing schedules (allocation ratio 1:1:1:1, total subjects = 120). To ensure randomization of equal number of subjects to both nebulizers, block size of 8 will be used. To ensure equitable representation of gestational ages, GA stratum-specific randomization lists will be generated. Stratified block randomization will ensure balanced and independent distribution of participants within each dose group, avoid systematic differences between dose groups with respect to known or unknown confounding baseline variables, remove selection bias and control temporal trends^{2,62-66}. The balance resulting from blocked stratification can improve the power of trials by reducing unwanted variation, reduce Type I and II error rates, increase efficiency, and improve subgroup analyses.

The structure of Table 10 shows breakdown of the sample by confounding variables in rows (GA [stratifying factor] & nebulizer type [blocking factor]) with columns representing treatment groups. Therneau showed that balance in covariates begins to fail when the number of blocks approaches half the sample size (n/2)^{64,67}. Therefore studies using stratified assignment should not attempt to balance on

Table 10: Stratified Block Randomization of Sample

GA Group (Strata)	Nebulizer Device (Blocks)	Dosing Schedule			
		I	II	III	IV
24 0/7 – 28 6/7 (Extremely PT) ⁶¹	MiniHeart	5	5	5	5
	AeroNeb	5	5	5	5
29 0/7 – 32 6/7 (Very PT)	MiniHeart	5	5	5	5
	AeroNeb	5	5	5	5
33 0/7 – 36 6/7 (Moderately PT)	MiniHeart	5	5	5	5
	AeroNeb	5	5	5	5
Total		30	30	30	30

more than 2 to 3 important factors. In this study we have balanced 2 important factors (GA, nebulizer type); the resulting number of blocks (3 GA strata x 2 nebulizers x 4 dosing schedule groups=24) is <n/2 (120/2=60).

Multiple births, common in this premature population, will be randomized independently and not as a unit as the latter can lead to bias in the randomization process.

1.1.4.7. Allocation Concealment:

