	0.35	0.27	0.44	$\pm 8\%$
	0.40	0.32	0.49	$\pm 9\%$

Type I error of 0.05, two-tailed test

Sample Size Based on the Null Hypothesis & Error Rates:

We will also compare the primary efficacy outcome to that of historical controls. The eligibility criteria, baseline factors, clinical management protocols, criteria for NIV and MV, & outcomes in our study are similar to those of recently published clinical trials. The use of historic controls will decrease sample size, shorten duration, and enhance efficiency of our Phase II study; definitely an advantage for testing four dosing regimens in this orphan population^{1,90-94}. Additionally, since AS has been shown to be potentially beneficial, this will allow all patients to receive study medication early and non-invasively thus enhancing study feasibility.

The rate of intubation following NIV for RDS among 24-36 weeks GA PT infants is ~50%^{75,95}. We estimated a 50% relative risk reduction to be clinically significant and plausible based on our preliminary data & reports in literature. Studies of MIST during NIV in PT infants 24- 36 weeks GA with RDS show an absolute risk reduction of the need for MV of 10-50% and a relative risk reduction of 21-63% (RR 0.67, 95% CI 0.57, 0.79) with a lower treatment threshold (FiO₂≤0.45) conferring a greater advantage (RR 0.72, 95% CI 0.59, 0.87) compared to a higher threshold (FiO₂>0.45) (RR 0.55, 95% CI 0.40, 0.77)^{5,33,75,92,93,95-104}.

A sample size of 30 subjects within each dose schedule group will have 81.8% power to detect a relative risk reduction of 50% (absolute risk reduction 25%) in the primary outcome of the need for intubation in 72 hours compared to a historical control value of 0.5 in a two-tailed type I error rate of 0.05 (Table 13).

Collapsing dilution groups corresponding to dose of 100 mg/kg & 200 mg/kg or considering our entire sample of 120 subjects all of whom receive AS will allow us to detect a smaller effect size with greater power.

An alternative strategy for sample size of Phase II trials is to reduce the level of rigor required by increasing the Type I error rate to as large as 25%^{90,105}. This increases the risk of erroneously concluding that the treatment is worthy of further investigation but does not increase the risk of missing an efficacious treatment. This approach would allow us to evaluate the effect sizes in Table 13 with smaller sample sizes.

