The DMC met on 02-22-2017 and recommended continuing subject accrual in the lowest GA Stratum (I) till Dec 2017. In addition, the DMC recommended continuing subject accrual in the two higher GA Strata subject to availability of resources; enrollment in excess will increase power and confidence in the results.

We proposed increasing the sample size by 40 to account for additional infants to be enrolled in the two higher GA strata till Dec 2017 or when 40 subjects have been accrued in Stratum I, whichever comes earlier. In addition we requested that the sample size for the study be increased by 20 to accommodate for current and future screen failures (estimating a maximum of 10 screen failures in the future). These two changes will increase the total sample size of the Phase II portion of the study to 220 subjects, and overall sample size of the study including the 17 subjects enrolled in the Phase I portion of the study will be 237.

1.1.11. Patient Population Available for the Single Center Phase II study:

This study will be performed primarily at HWH, a level III neonatal intensive care unit (NICU) and high risk maternal referral center. Numbers of infants 24^{0/7} – 36^{6/7} weeks GA treated for RDS are estimated from the data presented in Section 3.3.3. The goal is to enroll 120 subjects over 3 years. Given the statistics for the past 2 years an adequate population of infants is available even after considering a continued trend for declining birth rate, 10% need for intubation in delivery room and a conservative estimate of consent rate of 50%.

Table 14: Patient Population Available for Study:

GA	Admissions at HWH			Estimates of infants requiring treatment for RDS (%)*		Estimates of Projected # of infants requiring treatment for RDS at HWH (n)			
						Over 2 years		Over 3 Years	
	2011	2012	Total	Lower	Higher	Lower	Higher	Lower	Higher
24-28	76	76	152	0.38	1.00	58	152	87	228
29-32	120	103	223	0.27	0.62	60	138	90	207
33-36	462	462	924	0.10	0.18	88	166	132	249
Total	658	641	1299			206	457	309	685

* based on Table 2; shaded rows represent population of interest for this study

1.1.12. Statistical Analyses:

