Analysis plan to address Aim #2: - Determination of Optimal Dilution and Dosage of AS: The optimum dose is one that produces low toxicity while nearly maximizing the biological response⁸⁹. The optimal dosage will be determined by comparing levels of adverse responses, feasibility items and primary and secondary efficacy treatment outcomes (rates of intubation, diagnosis of PDA, need for blood transfusions, postnatal growth, duration of respiratory support, length of hospital stay, and incidence of complications of prematurity including IVH, sepsis, pneumonia, BPD, NEC, ROP, and death) across the four dosing schedules (Appendix IX, Mock Tables). The optimal dosage/dilution will be the one with the minimum level of adverse responses and highest clinical treatment outcomes.

Analysis plan to address Aim #3 - Short-term efficacy of AS: The primary outcome variable for short-term efficacy is the need for intubation & MV within 72 hours of AS. We will estimate the unconditional probability of benefit for the four dosing schedule groups (I, II, III, IV), the 2 dose groups (100 vs. 200 mg/kg) and the entire study cohort of 120 subjects. We will also compare with reported rates of intubation in historical controls (50%). A special χ^2 test to compare sample proportion with population proportion will be conducted to test the study hypothesis that AS is efficacious. In the comparison analysis, different dosages/dilutions will also be considered as weight using the “optimal” dosage/dilution obtained from Aim #2 as reference. A significantly lower rate of intubation in infants treated with AS in this study as compared to the reported rate of ~0.5 at $p < 0.05$ level (two-sided) will be used as evidence supporting the efficacy of AS. However, it is likely we may not

have power to achieve statistically significant results. Nevertheless these preliminary efficacy data will be crucial in determining outcome measures and effect size for the definitive placebo-controlled Phase III trial.

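### Siblings are randomized individually but analysed as independent, so the pooled comparison with 0.5 may be modestly too precise

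*Combined protocol and SAP*

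**What the plan says.** Section 1.1.4.6 (Randomization Procedures) states: "Multiple births, common in this premature population, will be randomized independently and not as a unit". Its reason is that randomizing a sibling set as a unit could bias the allocation. The design there is "allocation ratio 1:1:1:1, total subjects = 120", stratified by GA. Section 1.1.10 later raises the "total sample size of the Phase II portion of the study to 220 subjects".

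For efficacy, section 1.1.12 (Aim #3) plans a special chi-square "test to compare sample proportion with population proportion will be conducted to test the study hypothesis that AS is efficacious". A significantly lower intubation rate than about 0.5 at the 0.05 "level (two-sided) will be used as evidence supporting the efficacy of AS". Table 12 gives single-group confidence intervals from a binomial formula. Table 13 gives power "compared to a historical control value of 0.5 in a two-tailed type I error rate of 0.05".

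The other methods named in section 1.1.12 are chi-square, t-tests, ANOVA, nonparametric tests and logistic regression. Longitudinal analysis is mentioned only for measurements repeated over time. Neither the list of adjustment covariates nor the analyses added by the data monitoring committee includes a mother, sibling or multiple-birth term. The public text mentions no GEE, random effect, robust variance or design effect.

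**The concern.** The plan foresees siblings at randomization but does not carry them into the analysis. Siblings share GA, which the plan stratifies on because more immature infants are intubated more often. They generally share antenatal steroid exposure, which the plan lists as a covariate. A positive correlation in intubation is therefore plausible.

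The issue is sharpest for the pooled test against 0.5. Every infant receives aerosolized surfactant, so enrolled siblings always fall in the same analysed group and individual randomization gives no protection. With positive correlation the plain binomial variance is then too small, unless something offsets it. At stake are the pooled confidence interval, the p < 0.05 evidence rule, and the precision of an estimate meant to inform the Phase III effect size.

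**Working it through.** **1. The plan's own figures.** Table 13 can be reproduced by treating every infant as independent: power = Phi(|2 asin(sqrt p1) - 2 asin(sqrt 0.5)| x sqrt(n) - 1.96). This gives 81.8% (n = 30, rate 0.25), 98.2% and 89.0% (n = 60, rates 0.25 and 0.30), and 99.99%, 99.5% and 91.6% (n = 120, rates 0.25, 0.30 and 0.35). All six rows agree with the plan, to rounding or truncation, so the table contains no sibling allowance.

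**2. Inputs.** From the documents: null rate 0.5, two-sided alpha 0.05, and groups of 30, 60 and 120. Assumed, because the documents say only that multiples are common: s, the share of infants with an enrolled sibling, 0.15-0.40; and ICC, the sibling correlation of intubation, 0.2-0.6. All sibling sets are taken as pairs.

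**3. Formulas.** Design effect DE = 1 + s x q x ICC, where q is the chance that a sibling falls in the same analysed group: 1 for the pooled cohort, about 1/2 per dose and about 1/4 per schedule. True alpha of the planned test = 2 x (1 - Phi(1.96/sqrt DE)).

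| s, ICC | Pooled: DE, alpha | Per dose: DE, alpha | Per schedule: DE, alpha |
|---|---|---|---|
| 0.15, 0.2 | 1.03, 0.0535 | 1.015, 0.052 | 1.008, 0.051 |
| 0.30, 0.4 | 1.12, 0.064 | 1.06, 0.057 | 1.03, 0.0535 |
| 0.40, 0.6 | 1.24, 0.078 | 1.12, 0.064 | 1.06, 0.057 |

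Pooled intervals should be wider by sqrt(1.03) - 1 = 1.5% to sqrt(1.24) - 1 = 11%. DE does not depend on n, so raising the sample size neither cures nor worsens this.

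**4. Power of a corrected test.** Replace n by n/DE in the normal approximation. For n = 120 at rate 0.35, the uncorrected 91.8% becomes 91.0%, 88.5% and 85.1% in the three scenarios. For n = 30 at rate 0.25, the uncorrected 81.6% becomes about 81%, 80% and 79%.

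**5. Effect on a decision.** With 49 of 120 intubated, z = (0.4083 - 0.5)/sqrt(0.25/120) = -2.008 and p = 0.045. Dividing z by sqrt DE gives p = 0.048 at DE 1.03, 0.051 at 1.06, 0.061 at 1.15 and 0.071 at 1.24. With 48 of 120, p = 0.028 as planned and still 0.049 at DE 1.24.

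**6. Contrasts between schedules or doses.** The variance factor is 1 + s x ICC x (q - q'), where q' is the chance that the sibling is in the particular comparison group. With independent allocation q = q' and the factor is 1. For siblings in the same block of 8 (two places per schedule), q = 1/7 and q' = 2/7 for two schedules, or 3/7 and 4/7 for two doses. The factor is then 1 - s x ICC/7: 1 - 0.03/7 = 0.996 to 1 - 0.24/7 = 0.966. Ordinary standard errors are neutral or slightly conservative here.

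**7. Offset from GA stratification.** Table 10 plans 40 infants per stratum. Assume stratum rates of 0.7, 0.5 and 0.3. The mean within-stratum variance is (0.21 + 0.25 + 0.21)/3 = 0.2233, or 0.893 of the 0.25 used by the planned test. The remaining 0.0267 is variance between strata.

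- If the ICC is the correlation within stratum, the net factor is 0.893 x (1 + s x ICC).
- If it also includes the shared stratum, the net factor is [0.2233 + s x (0.25 x ICC - 0.0267)]/0.25.

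In the middle scenario these give 1.00 and 0.98, with alpha 0.050 and 0.048. In the low scenario alpha is about 0.04, and in the high scenario about 0.06.

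**The case against.** The strongest reply is that the size rests on two assumed numbers. Each sibling must separately meet the eligibility criteria in sections 1.1.2 and 1.1.3, so the share with an enrolled sibling could be well below the share of multiple births. This stands: the omission is certain, its size is not.

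The GA-stratum offset also stands in part. Correlation that arises only from a shared stratum adds no variance when stratum totals are fixed, and step 7 shows the inflation vanishing in the middle scenario. But the amendments described in section 1.1.10 loosened the stratum totals, the stratum rates are assumed, and correlation within a stratum remains.

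The per-schedule figures, which carry the 81.8% power statement, barely move. Consecutively listed siblings share a schedule with probability only about 7/8 x 1/7 + 1/8 x 1/4 = 0.16. Discreteness matters about as much: with independent infants the exact size of the planned test is 0.043 at n = 30 and 0.055 at n = 120. The plan also says that it is not powered for efficacy. That limits the consequence, but it does not justify the variance when p < 0.05 is the declared evidence rule.

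A reader might infer that individual randomization of siblings is an error, that all the planned p-values are too small, or that the power statements are materially wrong. The documents support none of these. Individual randomization is deliberate and reasonable, randomized contrasts are not anti-conservative, and the n = 30 rows lose at most two to three percentage points on these inputs.

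**Conclusion.** The point holds for the comparison with 0.5 and the single-group intervals, chiefly in the pooled cohort. If siblings are positively correlated within GA stratum, the pooled standard error may be modestly too small. On the assumed inputs alpha is about 0.054-0.078 before any stratification offset. That range is not an estimate for this trial, and the net effect could be close to nil. The effect is smaller per dose (alpha about 0.052-0.064) and minor per schedule (about 0.051-0.057). Only a borderline pooled conclusion could change. Comparisons on factors that siblings share, such as GA stratum or antenatal steroids in the adjusted model, do not have the protection that individual randomization gives to schedule contrasts. This is a cheap improvement to the analysis, not a flaw in the design.

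**What to change.** Keep individual randomization. In section 1.1.12:

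- For the pooled and per-dose comparisons with 0.5 and their confidence intervals, use a cluster-robust variance, or an intercept-only GEE, with mother as the cluster and with GA stratum accounted for in the variance.
- For the logistic models, use GEE clustered on mother, with GA stratum and nebulizer in the model.
- Report the number and size of enrolled sibling sets, so that readers can judge how much this matters.

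A sensitivity analysis with one infant per mother would add reassurance. The cost is some SAP wording, one maternal identifier in the analysis file and slightly wider intervals. No change to enrolment, allocation or data collection at the bedside is needed.
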